#### **4.3. Protocol Deviations**

A summary of important protocol deviations will be provided by the Clinical Operations group for subjects in the Safety Analysis Set.

## 5. BASELINE DATA

### 5.1. Demographics

Subject demographic variables (ie, age, sex, race, and ethnicity) will be summarized by genotype and overall and using descriptive statistics (n, mean, SD, median, Q1, Q3, minimum, and maximum) for age, and using the numbers and percentages of subjects for age categories (< 65 years, ≥ 65 years), sex, race, and ethnicity. Age is calculated in years at the date of initial study drug administration. If a subject did not receive study drug after enrollment, the subject's age will be calculated from the date that the subject signed the informed consent form. The summary of demographic data will be provided for the Safety Analysis Set.

A by-subject demographic listing, which includes the date the informed consent was signed, will be provided by subject ID number in ascending order.

### 5.2. Other Baseline Characteristics

Other baseline characteristics include:

- BMI ( $\text{kg}/\text{m}^2$ ) as a continuous variable and as categories (< 30  $\text{kg}/\text{m}^2$ , ≥ 30  $\text{kg}/\text{m}^2$ )
- HCV genotype and subtypes
- Cirrhosis (Cirrhosis or Absence of Cirrhosis)
- IL28B (CC, Non-CC (including CT, and TT))
- baseline HCV RNA as a continuous variable and as categories (< 800,000 IU/mL, ≥800,000 IU/mL)
- baseline ALT as a continuous variable and for categories ( $\leq 1.5 \times \text{ULN}$ ,  $> 1.5 \times \text{ULN}$ )
- prior HCV treatment experience (treatment naïve, treatment experienced)
- cirrhosis (presence, absence, missing) by prior HCV treatment experience (treatment naïve, treatment experienced)
- prior HCV treatment for treatment experienced subjects (direct acting antiviral [DAA] + pegylated interferon [Peg-IFN] + RBV, Peg-IFN + RBV, Other)
- prior HCV treatment response (nonresponse, relapse/breakthrough) for treatment experienced subjects
- estimated glomerular filtration rate (eGFR) using the Cockcroft-Gault equation

Estimated glomerular filtration rate will be calculated by the Cockcroft-Gault method:  
$$eGFR_{CG} \text{ (mL/min)} = [(140 - \text{age (yrs)}) \times \text{weight (kg)} \times (0.85 \text{ if female})] / (\text{serum creatinine (mg/dL)} \times 72)$$
, where weight is total body mass in kilograms.

These baseline characteristics will be summarized by genotype and overall using descriptive statistics (n, mean, SD, median, Q1, Q3, minimum, and maximum) for continuous variables and using the numbers and percentages of subjects for categorical variables. The summary of baseline characteristics will be provided for the Safety Analysis Set.

A by-subject listing of other baseline characteristics will be provided by subject ID number in ascending order.

A separate by-subject data listing for cirrhosis determination will be provided for all subjects at screening.

A separate by-subject data listing for prior HCV treatment and response will be provided for all treatment experienced subjects. The listing will display the prior HCV regimen(s) and treatment(s) including the treatment duration, and the prior HCV treatment response.

### **5.3. Medical History**

A by-subject listing of disease-specific medical history will be provided by subject ID number (in ascending order) and medical history of abnormalities (in chronological order).

## **6. EFFICACY ANALYSES**

### **6.1. Primary Efficacy Endpoint**

#### **6.1.1. Definition of the Primary Efficacy Endpoint**

The primary efficacy endpoint is SVR12 defined as HCV RNA < LLOQ 12 weeks after discontinuation of all study drugs in the FAS. The COBAS® AmpliPrep/COBAS® TaqMan® HCV Quantitative Test, v2.0 will be used to measure HCV RNA. The LLOQ for this assay is 15 IU/mL.

#### **6.1.2. Primary Analysis of the Primary Efficacy Endpoint**

The SVR12 rate in each of genotype will be calculated along with 2-sided 95% exact CI based on Clopper-Pearson method {Clopper 1934}.

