### 1.1. Study Objectives

The primary objectives of this study are:

- To evaluate the efficacy of treatment with sofosbuvir (SOF)/velpatasvir (VEL, GS-5816) fixed dose combination (FDC) for 12 weeks in subjects with chronic HCV infection as measured by the proportion of subjects with sustained viral response 12 weeks after cessation of treatment (SVR12)
- To evaluate the safety and tolerability of treatment with SOF/VEL for 12 weeks

The secondary objectives of this study are:

- To determine the proportion of subjects who attain SVR at 4 and 24 weeks after cessation of treatment (SVR4 and SVR24)
- To evaluate the kinetics of circulating HCV RNA during treatment and after cessation of treatment
- To evaluate the emergence of viral resistance to SOF and VEL during treatment and after cessation of treatment

The exploratory objectives of this study are:

PPD [REDACTED]

[REDACTED]

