### 1.3. Sample Size and Power

With a sample size of 120, the 95% exact confidence interval for different observed SVR12 rates are presented below:

Observed SVR12 rate	2-sided 95% exact CI
80% (96 out of 120)	72% - 87%
85% (102 out of 120)	77% - 91%
95% (114 out of 120)	89% - 98%

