#### **3.2. Subject Grouping**

For analyses based on the All Enrolled Analysis Set or FAS, subjects will be grouped according to the genotype (1a, 1b, 1 total and 3).

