#### **6.1.3. Subgroup Analysis of the Primary Efficacy Endpoint**

The point estimates and 95% exact CIs of the SVR12 rates will be displayed by genotype for subgroups outlined in Section 3.3.

A forest plot will graphically present estimates and 95% CIs in SVR12 rates for each of the subgroups.

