### 6.2.2. Analysis Methods for Secondary Efficacy Endpoints

For analyses of HCV RNA  $<$  LLOQ by visit while on treatment and during the posttreatment (SVR) follow-up period, subjects will be assigned a value at each visit based on the analysis visit windows specified in Section 3.6.2. Missing values will be imputed based on the categorical imputation rules described in Section 3.4.1. The 2-sided 95% exact CI based on Clopper-Pearson method will be provided for the percentage of subjects with HCV RNA  $<$  LLOQ at each visit within each genotype. The overall category for “HCV RNA  $<$  LLOQ” will be split into the following 2 subcategories: “ $<$  LLOQ TND” for subjects with target not detected and “ $<$  LLOQ detected” for subjects with  $<$  LLOQ in tabular displays.

Graphs for the percentage of subjects with HCV RNA  $<$  LLOQ over time during treatment will be displayed by genotype.

Summary statistics will be presented for absolute values and change from baseline in HCV RNA ( $\log_{10}$  IU/mL), by genotype and overall and by visit through EOT. Imputation rules described in Section 3.4.1 will be used to assign HCV RNA values for missing values at a visit that are bracketed by “ $<$  LLOQ TND” and/or “ $<$  LLOQ detected”. Otherwise, a missing = excluded analysis will be performed. Plots of the mean  $\pm$  SD and median (Q1, Q3) of absolute values and changes from baseline in HCV RNA through EOT will be presented.

For the SVR12 endpoint analysis, a summary table of the number and percentage of subjects with SVR12, virologic failure, and Other by genotype will be created. All subjects who achieve SVR12 will be categorized as SVR12. Virologic failure will be descriptively summarized as “on-treatment virologic failure” and relapse (which will be broken down by study drug completed yes/no). Subjects who do not achieve SVR12 and do not meet criteria for virologic failure will be categorized as “Other.” The denominator for relapse will be the number of subjects who had HCV RNA  $<$  LLOQ on their last observed on-treatment HCV RNA measurement; otherwise, the denominator will be the number of subjects in the FAS.

A concordance table between SVR12 and SVR24 will be provided for each genotype. Subjects with both observed SVR12 and observed SVR24 data will be included for this analysis.

Drug resistant substitutions will be analyzed and reported based on change from baseline sequence and/or change from HCV genotype reference strain.

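### The primary analysis gives SVR12 only within genotype; the all-subject rate behind the objective and the n=120 precision table is not planned anywhere in the SAP

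*SAP*

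**What the plan says.** Three parts of the SAP treat SVR12 as a matter for all subjects:

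- Section 1.1: the primary efficacy objective is to evaluate the regimen "in subjects with chronic HCV infection as measured by the proportion of subjects with sustained viral response 12 weeks after cessation of treatment", with no division by genotype.
- Section 6.1.1: the primary endpoint is "SVR12 defined as HCV RNA < LLOQ 12 weeks after discontinuation of all study drugs in the FAS".
- Section 1.3: "With a sample size of 120, the 95% exact confidence interval for different observed SVR12 rates are presented below". The three rows are 96, 102 and 114 responders out of 120, which is the whole planned enrolment in section 1.2.

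The analysis sections are written by genotype:

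- Section 3.2: for the All Enrolled Analysis Set and the FAS, "subjects will be grouped according to the genotype (1a, 1b, 1 total and 3". No all-subject group is listed.
- Section 6.1.2: "The SVR12 rate in each of genotype will be calculated along with 2-sided 95% exact CI based on Clopper-Pearson method".
- Section 6.1.3: subgroup estimates "will be displayed by genotype for subgroups outlined in Section 3.3".
- Section 6.2.2: "a summary table of the number and percentage of subjects with SVR12, virologic failure, and Other by genotype will be created". The rates of HCV RNA below LLOQ by visit, which include SVR4 and SVR24, and the SVR12–SVR24 concordance table are likewise specified per genotype.

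In the same section 6.2.2, continuous HCV RNA is to be summarised "by genotype and overall and by visit through EOT".

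**The concern.** Followed as written, the SAP yields separate SVR12 rates for genotypes 1a, 1b, 1 in total and 3. It yields no rate for the treated population as a whole. That pooled rate is the most direct answer to the objective in 1.1, and it is the only rate to which the intervals in 1.3 apply. A programmer working literally would put an overall column in the log10 HCV RNA table and none in the SVR12 table.

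Two things are at stake. First, the headline rate would have to be added later, outside the stated primary analysis. Second, the SAP points two ways on which rate is primary: the objective, endpoint and sample-size sections point to the pooled rate, and 6.1.2 points to the genotype rates. If the genotype rates are meant, section 1.3 overstates the precision to be expected at a given observed rate, because each genotype group holds only part of the 120.

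There is also a smaller gap. A subject with a genotype other than 1 or 3 would be in the FAS but in none of the groups in 3.2. Eligibility is not shown, so whether this can happen is unknown.

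**Working it through.** **Inputs.** n = 120 and the responder counts 96, 102 and 114 are from section 1.3. The two-sided 95% Clopper-Pearson method is from section 6.1.2. The genotype groups are from section 3.2. The SAP gives no genotype group sizes, so those used below are assumptions.

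**Formula.** For x responders among n, with B(p; a, b) the p-quantile of the beta distribution:

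- lower limit = B(0.025; x, n − x + 1)
- upper limit = B(0.975; x + 1, n − x)

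**Step 1: reproduce section 1.3.**

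| x/n | Computed 95% CI | Stated in 1.3 | Width (points) |
|---|---|---|---|
| 96/120 | 71.7–86.7% | 72–87% | 15.0 |
| 102/120 | 77.3–90.9% | 77–91% | 13.5 |
| 114/120 | 89.4–98.1% | 89–98% | 8.7 |

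All three rows agree after rounding. The table is arithmetically right, for a rate with 120 in the denominator.

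**Step 2: look for that rate among the planned analyses.**

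| SAP section | Display | All-subject figure named? |
|---|---|---|
| 4.1 | Disposition | Yes |
| 4.2.1 | Exposure | Yes |
| 4.2.2 | Adherence | No |
| 5.1, 5.2 | Demographics, baseline characteristics | Yes |
| 6.1.2 | SVR12, primary analysis | No |
| 6.1.3 | SVR12 subgroup estimates | No |
| 6.2.2 | HCV RNA below LLOQ by visit, including SVR4 and SVR24 | No |
| 6.2.2 | SVR12 / virologic failure / Other | No |
| 6.2.2 | SVR12–SVR24 concordance | No |
| 6.2.2 | Continuous HCV RNA | Yes |

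Three wordings come close and do not supply it. The genotype 1 total leaves out genotype 3. The reference to the FAS in 6.1.1, and the FAS denominator in 6.2.2, fix the population, but sections 3.1.2 and 3.2 then group the FAS by genotype. The forest-plot sentence in 6.1.3 carries no genotype restriction, but it covers subgroups and names no overall estimate.

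**Step 3: precision of the rates that are planned.** Relative width is the interval width divided by the n=120 width at the same observed rate (8.71 points at 95%, 13.53 at 85%).

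| Assumed n | 95% observed: CI | Width | Relative | 85% observed: CI | Width | Relative |
|---|---|---|---|---|---|---|
| 120 | 89.4–98.1% | 8.7 | 1.00 | 77.3–90.9% | 13.5 | 1.00 |
| 80 | 87.7–98.6% | 10.9 | 1.26 | 75.3–92.0% | 16.7 | 1.24 |
| 60 | 86.1–99.0% | 12.9 | 1.48 | 73.4–92.9% | 19.5 | 1.44 |
| 40 | 83.1–99.4% | 16.3 | 1.87 | 70.2–94.3% | 24.1 | 1.78 |
| 20 | 75.1–99.9% | 24.7 | 2.84 | 62.1–96.8% | 34.7 | 2.56 |

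**Step 4: a bound that needs no exact split.** Suppose all 120 subjects have genotype 1 or 3. The larger of the two groups then has at least 60 subjects and the smaller at most 60. At 95% observed in the group, the larger group's interval is at most about 12.9 / 8.7 ≈ 1.5 times as wide as the 95% row of 1.3, and the smaller group's is at least about 1.5 times as wide. At 85% observed the corresponding factor is 19.5 / 13.5 ≈ 1.44. Groups 1a and 1b are parts of the genotype 1 total and can only be smaller than it.

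**The case against.** The strongest reply is that little is left open. The population, endpoint, LLOQ, visit windows, record selection, imputation and interval method are all fixed. If only genotypes 1 and 3 are enrolled, the pooled count is the sum of the genotype 1 total and genotype 3, and its exact interval follows without discretion. On this view only a table column is missing. This stands as a limit on the harm: adding the pooled rate late gives little room to influence its value. It does not settle which rate is primary, and it does not make the SAP produce the rate.

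A second reply is that 6.1.2, read literally, makes the genotype rates primary, and that the objective does not demand a single pooled number. That reading is possible. Section 1.3 would then give precision for a rate that is not analysed, so the SAP needs correcting either way.

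Third, the omission may be loose drafting. The adherence summary in 4.2.2 also lacks an overall figure, although exposure in 4.2.1 has one, and section 3.3 lists HCV genotype among subsets to be examined within genotype. This is fair: the text does not show whether the omission was deliberate.

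Fourth, the comparison of widths depends on the observed rate. With every subject responding, 60/60 gives 94.0–100% (6.0 points), narrower than the 8.7 points for 114/120. The factors above therefore hold only when the same observed rate is compared. Finally, the protocol is not shown and may plan the pooled rate. Section 6.4 declares no changes from it, but that does not reconcile 6.1.2 with 1.3 inside the SAP.

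**Conclusion.** The concern holds and should be fixed. The SAP justifies its sample size by the precision of an all-subject SVR12 rate and then plans SVR12 only within genotype, so the estimate in 1.3 is never specified. At 95% observed, the planned intervals would be about 1.5 times as wide as 1.3 shows for a group of 60, 1.9 times for 40 and 2.8 times for 20. These factors rest on assumed group sizes and on comparing equal observed rates.

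The consequence is limited. The analysis is descriptive, the SAP states no SVR12 test or threshold, and the intervals in 1.3 are correct for the pooled rate. An overall row may well be produced in practice, but the SAP does not say so.

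**What to change.** - **6.1.2:** add the SVR12 rate in all FAS subjects with its two-sided 95% Clopper-Pearson interval, next to the genotype rates, and state which is primary.
- **3.2:** add an all-subject group, so that every FAS subject counts in the overall figure whatever the genotype.
- **6.1.3 and 6.2.2:** carry that group into the SVR12 subgroup display, the by-visit rates (including SVR4 and SVR24), the SVR12 / virologic failure / Other table and the concordance table.
- **1.3:** label the intervals as applying to the overall rate. If the genotype rates are declared primary, replace them with intervals for the expected genotype group sizes.

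The cost is SAP wording and one extra column in tables already planned, with no new data or subjects. If the genotype rates are made primary, section 1.3 will show wider intervals than it does now at the same observed rates.

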#### **6.1.3. Subgroup Analysis of the Primary Efficacy Endpoint**

The point estimates and 95% exact CIs of the SVR12 rates will be displayed by genotype for subgroups outlined in Section 3.3.

A forest plot will graphically present estimates and 95% CIs in SVR12 rates for each of the subgroups.

### **6.2. Secondary Efficacy Endpoints**

#### **6.2.1. Definition of Secondary Efficacy Endpoints**

Secondary efficacy endpoints include the following:

- The percentage of subjects with HCV RNA < LLOQ at 4 and 24 weeks after discontinuation of treatment (SVR4 and SVR24)
- The percentage of subjects with HCV RNA < LLOQ while on treatment by study visit
- HCV RNA ( $\log_{10}$  IU/mL) and change from baseline in HCV RNA ( $\log_{10}$  IU/mL) through end of treatment (EOT)
- The percentage of subjects with virologic failure as the following:
  - On-treatment virologic failure
    - HCV RNA  $\geq$  LLOQ after having previously had HCV RNA < LLOQ, while on treatment, confirmed with 2 consecutive values (note, second confirmation value can be posttreatment), or last available on-treatment measurement with no subsequent follow up values (ie, breakthrough)

- $> 1 \log_{10}$  IU/mL increase in HCV RNA from nadir while on treatment, confirmed with 2 consecutive values (note, second confirmation value can be posttreatment), or last available on-treatment measurement with no subsequent follow up values (ie, rebound)
- HCV RNA persistently  $\geq$  LLOQ through 8 weeks of treatment (ie, nonresponse)

— Relapse

- HCV RNA  $\geq$  LLOQ during the posttreatment period having achieved HCV RNA  $<$  LLOQ at end of treatment, confirmed with 2 consecutive values or last available posttreatment measurement
- Characterization of HCV drug resistance substitutions at baseline, during, and after therapy with SOF/VEL

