### 1.2. Study Design

This is a multi-center, open-label study of adult subjects with chronic HCV that will evaluate the safety, tolerability and antiviral efficacy of SOF/VEL FDC for 12 weeks in subjects with chronic HCV infection.

Approximately 120 subjects will be enrolled to receive: SOF/VEL (400 mg/100 mg) once daily for 12 weeks.

Up to 20% of subjects enrolled in the study may have cirrhosis at baseline and up to approximately 20% may be treatment-experienced.

The total time to complete all study visits is approximately 40 weeks including:

- 28 day (4 weeks) screening period (or can be extended to 42 days)
- 12 week treatment period
- Up to 24 week posttreatment period

The schedule of assessments is provided as an appendix to the SAP (Appendix 1).

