## **11. APPENDICES**

Appendix 1      Schedule of Assessments

**Appendix 1 Schedule of Assessments**

**Appendix Table 1. Screening, On-Treatment Visits**

	Screening (Day -28 to Day 0)	Day 1	On-treatment Study Week (± 3 days)					Post treatment Study Week (± 5 days) i		
			1	2	4	8	12/ET	4	12	24
Clinical Assessments										
Informed Consent	X									
Determine Eligibility	X	X								
Medical History	X	X								
Physical Examination	X	X					X			
Height	X									
Weight	X	X					X	X		
Vital Signs b	X	X	X	X	X	X	X	X		
12-Lead ECG c	X	X	X				X			
AEs	X	X	X	X	X	X	X	X		
Concomitant Medications	X	X	X	X	X	X	X	X		
Pregnancy Prevention Counseling		X			X		X	X		
Health Related Quality of Life Survey, SF-36		X			X		X	X	X	
Review of Study Medication Compliance g			X	X	X	X	X			
Study Drug Dispensing a		X			X	X				

	Screening (Day -28 to Day 0)	Day 1	On-treatment Study Week (± 3 days)					Post treatment Study Week (± 5 days) i		
			1	2	4	8	12/ET	4	12	24
Laboratory Assessments										
Hematology, Chemistry	X	X	X	X	X	X	X	X	X	
Coagulation Tests	X	X					X			
HCV RNA	X	X	X	X	X	X	X	X	X	X
Viral Sequencing		X	X	X	X	X	X	X	X	X
Pregnancy Testing d	X	X			X	X	X	X		
Urinalysis, Urine Drug Screen	X									
HCV Genotyping,	X									
HCV, HIV, HBV Serology	X									
HbA1c, Cirrhosis assessment (Fibrotest ® and APRI)	X									
Optional Archive Sample f		X					X			
IL28B		X								
Pharmacogenomic Sample e		X								
Imaging for Hepatocellular Carcinoma (HCC)	X									

- a. Day 1 assessments must be performed prior to the first dose of the study drug(s)
- b. Vital signs include resting blood pressure, pulse, respiratory rate and temperature.
- c. Subjects will be required to rest in a supine position for ≥ 5 minutes prior to making a recording. The investigator (or qualified designee) should review the ECG traces recorded in real time for gross abnormalities.
- d. For female of child bearing potential only. Serum β-hCG at screening, urine pregnancy test on Day 1 and every 4 weeks on treatment visits.
- e. For subjects who provide their additional and specific consent, an optional blood sample will be collected at the Baseline/Day 1 visit for PG (this sample may be drawn after Baseline/Day 1 if necessary).
- f. Subjects may opt out of archive sample collection.

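### Relapse is defined by HCV RNA alone, so a reinfection seen by the Week 12 follow-up window is reported as SOF/VEL relapse, and the scheduled sequences are not used to separate the two

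*SAP*

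**What the plan says.** Relapse (SAP Section 6.2.1) is quantifiable HCV RNA in the posttreatment period in a subject who was below "LLOQ at end of treatment, confirmed with 2 consecutive values or last available posttreatment measurement". The threshold comes from Section 6.1.1: "The LLOQ for this assay is 15 IU/mL". The rule has no genotype, subtype or sequence criterion.

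The SVR12 outcome table (Section 6.2.2) has three destinations: SVR12, virologic failure (on-treatment failure or relapse) and Other. Anyone who achieves SVR12 goes to SVR12. Entry to Other is restricted: "Subjects who do not achieve SVR12 and do not meet criteria for virologic failure will be categorized as" Other. The relapse denominator is the subjects below LLOQ at their last observed on-treatment value.

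A secondary objective (Section 1.1) is "To evaluate the emergence of viral resistance to SOF and VEL during treatment and after cessation of treatment". The whole analysis method for it is one sentence in Section 6.2.2: "Drug resistant substitutions will be analyzed and reported based on change from baseline sequence and/or change from HCV genotype reference strain".

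Appendix Table 1 marks "Viral Sequencing" at Day 1, at every on-treatment visit and at posttreatment Weeks 4, 12 and 24. HCV genotyping is marked at screening only. Nothing in the readable text mentions reinfection or a check that the posttreatment virus is the baseline strain.

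**The concern.** The label relapse implies that the drug failed to eradicate the treated virus. The SAP's rule observes only that virus is present again. A reinfected subject meets the rule, and because Other is closed to anyone who meets it, the classification leaves no discretion.

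Two secondary outputs are exposed. The relapse and virologic failure percentages would contain an event that is not a failure of the regimen. In the resistance analysis, a comparison with the baseline sequence shows emergence only if the posttreatment virus descends from the baseline virus. With a different strain, a pre-existing difference at a resistance position can be reported as change from baseline. If the genotype has also changed, the SAP does not say which reference strain applies.

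Both outputs rest on few subjects when SVR12 is high, and they are reported by genotype. The study is also open-label with a single regimen, so moving a failure to reinfection after the results are known would look data-driven. The rule therefore needs to be fixed in advance.

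**Working it through.** **1. The plan's own figures.** Inputs: "Approximately 120 subjects will be enrolled to receive" SOF/VEL (Section 1.2), and a "2-sided 95% exact CI based on Clopper-Pearson method" (Section 6.1.2). For x events in n, the lower limit is the 0.025 quantile of Beta(x, n − x + 1) and the upper limit is the 0.975 quantile of Beta(x + 1, n − x).

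- 96/120: 71.7% to 86.8% (SAP Section 1.3: 72% to 87%)
- 102/120: 77.3% to 90.9% (SAP: 77% to 91%)
- 114/120: 89.4% to 98.1% (SAP: 89% to 98%)

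All three agree after rounding. The SAP states no relapse or reinfection rate, so there is no further figure to reproduce.

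**2. A reinfection traced through the rules.** Take a subject below LLOQ at end of treatment whose later viraemia is confirmed or is the last available value.

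- *Seen by the FU-12 window.* For HCV RNA this window is follow-up days 70 to 146 (Table 3-2), and the latest record in it is used (Section 3.6.3). If that value is at or above LLOQ, SVR12 is not achieved, the relapse rule is met and Other is closed. The subject is reported as relapse.
- *First seen in the FU-24 window (days 147 to 210).* SVR12 was achieved, so the subject stays in the SVR12 row. The Section 6.2.1 relapse definition, which covers the whole posttreatment period, is still met. The subject counts against SVR24 and is discordant in the SVR12/SVR24 concordance table.

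**3. Effect on the relapse rate.** The illustration uses the SAP's 114/120 scenario, which leaves 120 − 114 = 6 non-responders. It assumes that all 6 meet the relapse rule and that the relapse denominator is 120. Each reinfection counted as relapse contributes 1/120 = 0.83 percentage points.

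| Reinfections among the 6 | Relapse after separation | Exact 95% CI |
|---|---|---|
| 0 (as written) | 6/120 = 5.0% | 1.9 to 10.6 |
| 1 | 5/120 = 4.2% | 1.4 to 9.5 |
| 2 | 4/120 = 3.3% | 0.9 to 8.3 |

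SVR12 stays at 114/120 = 95.0% (89.4 to 98.1) in every row, because a reinfected subject remains a non-responder.

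**4. Within a genotype.** Group sizes are not given. In an assumed group of 40, one case is 1/40 = 2.5 points: 2/40 = 5.0% (0.6 to 16.9) becomes 1/40 = 2.5% (0.1 to 13.2).

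**5. How many reinfections to expect.** The SAP gives no rate, so a range is assumed. Expected count = 120 × (days/365.25) × (rate/100), with all 120 at risk throughout. That is 27.6 person-years over 84 days and 55.2 over 168 days.

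| Assumed rate per 100 person-years | 84 days | 168 days |
|---|---|---|
| 0.5 | 0.14 | 0.28 |
| 1 | 0.28 | 0.55 |
| 2 | 0.55 | 1.1 |
| 5 | 1.4 | 2.8 |
| 10 | 2.8 | 5.5 |

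**The case against.** The strongest reply is that this concerns descriptive secondary outputs and possibly no subject at all. At assumed rates of 0.5 to 2 per 100 person-years, fewer than one reinfection is expected over 84 days. One case moves 5.0% to 4.2% with intervals that nearly coincide, and no test or margin depends on it. The present rule also errs against the drug. All of that stands, and it limits the importance of the point.

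A second reply is that the protocol, which is not at hand, may deal with reinfection. It may. But the SAP refers to no such rule, and its own definition admits no exception.

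A third is that comparison with the baseline sequence is already planned, so a genotype switch would probably be noticed. That is likely. What is missing is a decision rule and a place to report the result.

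A fourth is that sequence comparison may not separate reinfection from a minority strain already present at baseline, so a true failure could be moved out in the drug's favour. This is a fair warning, and the fix must answer it.

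Several stronger readings are not supported:

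- A reader might infer that any reinfection during the 24-week follow-up is filed as virologic failure in the outcome table. It is not: SVR12 takes precedence, so one first seen after the FU-12 window stays in the SVR12 row.
- A reader might infer that the SAP treats SVR12/SVR24 discordance as late relapse. It plans a plain table of observed data and attributes no cause.
- A reader might infer that all strain differences would be reported as emerging on treatment. Section 6.2.2 concerns drug-resistant substitutions only, and has no rule labelling every change as on-treatment emergence.

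**Conclusion.** The point holds for the relapse, virologic failure and resistance outputs. Sections 6.2.1 and 6.2.2 together oblige the analyst to report a reinfection seen by the FU-12 window as relapse, and allow differences at resistance positions between two strains to be reported as change from baseline. A later reinfection does not alter the SVR12 outcome table, but it meets the relapse definition, counts against SVR24 and appears as discordance.

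The primary SVR12 estimate and its interval do not change. The size is about 0.8 percentage points per case out of 120, and more within a genotype column. It would be wrong to read the example as showing that one case is a sixth of the failures. That requires all 6 non-responders to be relapses, whereas Section 3.4.1 counts unbracketed missing HCV RNA as failure for SVR12, so some of the 6 could belong in Other. The number of reinfections, the genotype group of 40 and the relapse denominator of 120 are likewise assumptions, and zero reinfections is possible.

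The change is worth making before database finalization because the rule as written gives a wrong label and the sequencing that could correct it is already scheduled.

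**What to change.** Add to Sections 6.2.1 and 6.2.2:

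- For every subject meeting the relapse criteria, compare the posttreatment sequence with the Day 1 sequence by genotype/subtype and phylogenetic analysis. Fix the criterion for a distinct strain before database finalization.
- Report a confirmed distinct strain as reinfection, on its own line of the outcome table.
- Keep that subject as a non-responder for each SVR endpoint at which HCV RNA is at or above LLOQ, and in the relapse denominator. Remove the subject from the relapse numerator.
- Exclude the subject from the summary of emergent substitutions, but list the sequence findings.
- If sequencing fails or is inconclusive, including a possible minority strain already present at baseline, assume relapse.
- Flag reinfections in the SVR12/SVR24 concordance table.

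The cost is a few sentences, one table row, a flag and a sequence comparison for the few subjects who meet the relapse rule. No new visits or samples are needed. The residual risk, a true relapse reclassified in the drug's favour, is limited by fixing the criterion in advance and by defaulting to relapse.
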